## 2 Objectives and Purpose

### **Aim 1. To evaluate the short- and longer-term effectiveness of PD and PDT.**

Hypotheses: (a) PD, implemented using localized scalable approaches, is more effective than control; and (b) PDT is more effective for CHWs/teachers than PD alone; and (c) PDT has a more favorable cost-effectiveness ratio than PD alone.

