## 9 Statistical Considerations

**Data Analysis Plan for Aim 1.** Prior to any outcome analyses, we will generate summary statistics for all data, summarizing with means and standard deviations for continuous variables and frequencies for categorical variables. The distribution of study variables and missing data patterns will be inspected. To estimate effectiveness, we will apply intention-to-treat (ITT) analyses and first focus on between-subject comparisons of intervention vs. control (comparing *PD* to control, comparing *PDT* to control, and comparing *PD* to *PDT*). We will estimate the impact of *PD* on children and teachers post-intervention (T2, 4-5 months after T1) and at one-year follow up (T3, 18 months after T1, or 12 months after T2). **Figure 4** below describe the model to be tested under Aim 1. School and class nesting will be considered, and a multiple imputation strategy will be applied to account for missing data. Linear mixed effect models, using SAS PROC MIXED, will be applied to examine short and longer-term impacts. We will first examine the immediate impact by modeling post-intervention outcomes (T2) as a function of intervention, adjusting for T1 outcome measures. The model accounts for between-subject (within-school and -class) correlation by including school- and classroom-level (when appropriate) random intercepts. The outcomes will be modeled as:  $Y_{ij} = \beta_1 I_j + \beta_2 C + \beta_3 X_{ij} + \gamma_j + \gamma_k + \epsilon_{ijk}$ , where  $Y_{ij}$  is the outcome for the student  $i$  in school  $j$ .  $I_j$  is intervention status (a categorical variable, with 3 levels) for school  $j$ , representing two dummy variables (control as the reference).  $C$  is the cohort indicator for

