school, where  $C=1$  if is in the second cohort, 0 for the 1st cohort.  $X_{ij}$  is the baseline value of the outcome for student  $i$  in school  $j$ . In the models,  $\beta_1$  represents the intervention impact,  $\beta_2$  is the effect of the second cohort,  $\beta_3$  is the effect of baseline measure,  $\gamma_j$  is the school-level random effect and  $\gamma_k$  is the class-level random effect (when appropriate), and  $\epsilon_{ijk}$  is the error term for student  $i$  in school  $j$  and  $k$  class. Next, we will study longer-term effectiveness outcomes (T2 to T3) by applying growth curve models and using repeated assessments over time. In these growth models, we will add time-relevant parameters to the model above, including school-level random slopes. The post-baseline scores will be modeled as a linear function of time/slopes, intervention indicator, and intervention-by-time interactions, adjusting for T1 scores and cohort. The long-term outcome will be modeled as:  $Y_{ij} = \beta_1 I_j + \beta_2 t + \beta_3 I_j * t + \beta_4 C + \beta_5 X_{ij} + \gamma_j + \gamma_k + \epsilon_{ijk}$ . A significant  $\beta_3$  would indicate the effect of the intervention depends on time; in this case, we will estimate the slopes for each condition, and the difference between the conditions with respect to the mean outcome scores. The analytical methods that we propose have been applied successfully in our previous US and LMIC studies. Cost-effectiveness analysis of *PD* and *PDT* implementation models will be examined using approaches that have been applied in previous school-based and parenting-based child mental health promotion research. The analysis will center on incremental cost-effectiveness ratios (ICERs), where the numerator represents the cost difference between the intervention arms and the control, and the denominator represents the difference in average intervention effects. To that end, the cost-effectiveness analysis of the intervention will involve examining how much the *PD/PDT* intervention costs to achieve a unit of effect relative to the control group. The effects of the intervention will be estimated using the effect sizes  $d$  (standardized mean difference between comparison groups) from an ITT approach. For the effectiveness outcomes, we will use an effect size of 0.2-0.4 as a benchmark; this corresponds to a small to medium effect size according to Cohen. We will calculate the ICERs and compute the per-participant cost per 0.2-0.4 SD change for each effectiveness outcome. Reporting of the analysis will follow the Consolidated Health Economic Evaluation Reporting Standards (CHEERS).

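### Hypothesis 1(c) compares PDT with PD, but Section 9 defines cost-effectiveness ratios only against control and states no uncertainty, so the plan does not show what T-Wellness adds for its extra cost

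*Combined protocol and SAP*

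**What the plan says.** Section 2 (Aim 1) and the Protocol Summary both state hypothesis 1(c): "PDT has a more favorable cost-effectiveness ratio than PD alone". This is a contrast between the two active arms.

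The cost-effectiveness text in Section 9 (Data Analysis Plan for Aim 1) defines the incremental cost-effectiveness ratio differently. Of the two terms, "the numerator represents the cost difference between the intervention arms and the control", while "the denominator represents the difference in average intervention effects". The comparator is then repeated: the analysis asks what the "intervention costs to achieve a unit of effect relative to the control group". Effects are standardized mean differences from the intention-to-treat analysis. As a yardstick, "we will use an effect size of 0.2-0.4 as a benchmark", and the output is stated as "We will calculate the ICERs and compute the per-participant cost per 0.2-0.4 SD change for each effectiveness outcome".

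The visible text defines no PDT-versus-PD ratio. It names no interval, resampling, acceptability curve, threshold or decision rule for 1(c). The CHEERS standard is cited for reporting only. The one cost variation named, in Table 2, is with and without monitoring cost.

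The ingredients of a direct comparison are planned. Section 9 lists PD against PDT among the effectiveness contrasts, and Section 6.1 collects programme costs for PD and PDT.

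**The concern.** PD and PDT are alternatives, and PDT is PD plus T-Wellness. A ministry that can already run PD needs to know what the extra day and the extra sessions cost per additional unit of benefit. Two ratios against a common control are average figures for whole programmes. If PDT has the worse average ratio, T-Wellness may add benefit at a price some would pay, or it may add cost and no benefit. These call for opposite decisions, and the ranking treats them alike.

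The second case is plausible. Hypothesis 1(b) claims superiority of PDT over PD only for teachers, while ratios are to be computed for every effectiveness outcome, child outcomes included.

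Without a stated interval, a reader also cannot tell whether the observed ranking is more than chance.

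**Working it through.** The documents give no cost, cost-effectiveness ratio or intraclass correlation, so there is no planned figure to reproduce. What follows is an illustration under stated assumptions.

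**Inputs from the documents**
- 12 schools per arm, about 55 children per school (Protocol Summary).
- PDT has 4 workshop days against 3, and 15 coaching hours against 12 (Protocol Summary, Section 5).
- Effects in SD units, benchmark 0.2 to 0.4 (Section 9).

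**Assumptions**
- Cost per participant net of control: PD = 100; PDT = 125 (15/12 = 1.25) to 133.3 (4/3 = 1.33). A cost ratio of 1.10 is also tried, since some costs are shared.
- PD effect 0.30 SD in the cost examples; equal effects of 0.3 to 0.4 in the chance calculation.
- Intraclass correlation 0.05 to 0.10; baseline explains none or half of the variance.

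**Step 1: what the ranking requires.** Write C for cost, E for effect and k for the PDT/PD cost ratio. With positive effects, the PDT ratio is lower only if E(PDT) > k × E(PD). For E(PD) = 0.30 that is 1.25 × 0.30 = 0.375 to 1.333 × 0.30 = 0.40.

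**Step 2: two cases that rank the same way.** The PD ratio is 100/0.30 = 333 per SD.
- PDT effect 0.36: ratio 125/0.36 = 347 to 133.3/0.36 = 370. Direct increment: 25/0.06 = 417 to 33.3/0.06 = 555 per extra SD.
- PDT effect 0.28: ratio 125/0.28 = 446 to 133.3/0.28 = 476. PDT costs more and does less, so it is dominated.

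Both read as less favourable than PD.

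**Step 3: sensitivity to the assumed cost.** At a cost ratio of 1.10, a PDT effect of 0.36 gives 110/0.36 = 306 against 333, and PDT ranks better.

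**Step 4: what the ranking gets right.** If both effects are positive, PDT costs more and its ratio is lower, Step 1 gives E(PDT) > E(PD). The increment (C(PDT) − C(PD))/(E(PDT) − E(PD)) is then lower still. If the estimated PDT effect is at or below that of PD, a larger cost over an equal or smaller effect always gives a higher ratio.

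**Step 5: chance rankings.** Suppose the true effects both equal d, so PDT is truly dominated. The variance of an arm mean is v = (1 + 54 × ICC)/(12 × 55), multiplied by 0.5 if baseline explains half the variance. The ranking favours PDT when E(PDT) − k × E(PD) > 0. With a shared control arm the probability is Φ(−d(k − 1)/√(v(1 + k² + (k − 1)²))).
- Low end, ICC 0.05, d = 0.4, k = 1.333: v = 3.7/660 = 0.00561, probability 0.147.
- High end, ICC 0.10, d = 0.3, k = 1.25: v = 6.4/660 = 0.00970, probability 0.319, or 0.304 when both estimated effects must also be positive (400,000 simulated trials).
- With half the variance explained by baseline: 0.069 to 0.252.

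The range is therefore about 15 to 30% without baseline adjustment and about 7 to 25% with it.

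**The case against.** The strongest reply is that 1(c) is worded as a comparison of ratios, and two ratios against a common control, set side by side, are such a comparison. That stands. A reader might infer that 1(c) goes unanswered; the documents do not support this. What is missing is the incremental question behind the hypothesis.

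A reader might also infer that point ratios fail to detect dominance, or that their ordering is valid only when PDT is the more effective arm. Step 4 shows otherwise. With both estimated effects positive, an arm dominated in the estimates always has the worse ratio, and the simulation found no exception. The ranking does not hide dominance; it fails to distinguish it from a worthwhile but dearer add-on.

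The chance figures are sampling error, and changing the comparator alone would not cure them. With equal true effects, the estimated PDT−PD effect difference is positive in half of trials, so a bare point increment would mislead too. The figures argue for an interval. Section 9 also plans adjustment for the baseline outcome, so the lower range matters.

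The planned PD-versus-PDT effectiveness contrast would let a reader see a PDT effect no better than PD, though nothing ties it to cost. Finally, Section 9 refers to approaches in cited economic studies that were not available for this review, and Figure 4, whose title covers cost-effectiveness, is not shown and could not be checked.

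**Conclusion.** The point holds in a limited form. Section 9 defines the ratios against control, states that comparator twice, and names no uncertainty method, while 1(c) contrasts PDT with PD. The planned output can rank the two programmes but does not show what T-Wellness adds for its extra cost, and it leaves the reliability of the ranking unstated.

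Under the assumed costs, one verdict of less favourable covers both a gain at 417 to 555 per extra SD and outright dominance. The example depends on the cost ratio, and at 1.10 the first case reverses. Chance rankings in favour of a truly dominated PDT run at about 15 to 30%, or about 7 to 25% with a strong baseline covariate. Costs, intraclass correlations and explained variance are all assumptions. The missing definition and interval do not depend on them, subject to what Figure 4 may contain.

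**What to change.** In Section 9, add for 1(c) the direct increment, (PDT cost − PD cost)/(PDT effect − PD effect), on a named outcome and time point. It can use the PD-versus-PDT contrast already planned there and the programme costs collected under Section 6.1.

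Obtain its uncertainty by resampling whole schools within arm and region, carrying costs and effects together. Show the result on the cost-effectiveness plane, or as an acceptability curve over a range of threshold values, because an interval for the ratio itself is unstable when the effect difference is near zero. State that PDT will be reported as dominated if it costs more and is no more effective. Keep the two ratios against control as descriptive results.

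The cost is a few sentences and one resampling run, with no new data. The drawback is that the stated uncertainty will look less favourable than a single point ratio.

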**Figure 4. Aim 1 Effectiveness and Cost-Effectiveness Mechanisms**

**Data Analysis Plan for Aims 2.** For testing *PD/PDT* theory of change, Preacher's Multilevel Structural Equation Modeling (SEM) and MacKinnon's mediation model testing principles/strategies will be applied. Figure 5 below describes the model to be tested under Aim 2. Mediators (primary and secondary) will be examined separately. Only intermediate outcomes that show significant improvement will be examined in the mediation model testing. The mediation model will build on the effectiveness evaluation model (Aim 1 model), by including changing scores of mediators (T2-T1) and T2 to T3 child outcome trajectory because a mediation model is ideally tested in a design demonstrating time precedence in which the intervention occurs before the outcome. The mediation mechanism will be modeled as:  $Y_{ij} = \beta_1 I_j + \beta_2 t + \beta_3 I_j * t + \beta_4 M_j + \beta_5 C + \beta_6 X_{ij} + \gamma_j + \gamma_k + \epsilon_{ijk}$ .  $M_j$  is the value of the mediator at T2 and/or T3 for school  $j$ .  $\gamma_j$  and  $\gamma_k$  are the school- and class-level random effects. We will compare  $\beta_1$  and  $\beta_3$  from this model with the  $\beta_1$  and  $\beta_3$  from the effectiveness models that are not included the moderator ( $Y_{ij} = \beta_1 I_j + \beta_2 t + \beta_3 I_j * t + \beta_4 C + \beta_5 X_{ij} + \gamma_j + \gamma_k + \epsilon_{ijk}$ ). A significant effect of  $\beta_1$  and  $\beta_3$  in the mediation model will suggest a mediation effect. A conventional

[figure not shown]
Sober test described by Baron and Kenny will be applied next to test the significance of the mediation model. This modeling approach has been applied in our previous work. To confirm the model, Multilevel SEM will also be conducted (using Mplus).

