## 1.2 **Rationale**

This study involves efforts to advance the science of prevention in early childhood mental health in low-resource communities. We will investigate the effectiveness, practical implementation strategies, and underlying mechanisms of the *PD* in urban and rural Uganda. We will compare effectiveness of two *PD* implementation approaches (with and without T-Wellness) using a hybrid effectiveness-implementation CRCT. **Figure 3** shows the conceptual model for *PD* and *PDT* Theory of change in LMIC contexts, which considers *intermediate intervention effectiveness outcomes* (teacher EBI practice) and *distal effectiveness outcomes* (including primary child mental health outcomes and secondary child behavioral outcomes, defined in Table 2). *PD* is expected to change teachers' EBI practices; and the impact of *PD* on distal child mental health outcomes will be mediated primarily through changes in teachers' practice of EBI strategies. Similarly, we expect that *PDT (PD+T-Wellness)* will also have impact on distal child mental health outcomes, and this will be mediated primarily through improvement in both teachers' EBI practices/behaviors and teachers' stress management skills (cognitive and behavioral control/ coping of stress). We anticipate *changes in child behaviors will be observed in the secondary outcome domains before the mental health outcomes* (primary distal outcomes). Because *PD/PDT* will be implemented in diverse contexts, our theory of change also considers moderators from aspects of the Consolidated Framework for Implementation Research (CFIR), which proposes that five domains of contextual factors can impact effectiveness-implementation. Specifically, we expect that certain *individual, intervention implementation, and school contexts* may also influence (or moderate) intervention effectiveness. We consider geographic region (urban/ rural) as the primary moderator, and other CFIR factors listed in the figure as secondary moderators. This theory of change has been partially tested (constructs in 'red' in Figure 3) and supported in previous *PD* studies. This study will formally examine the cost-effectiveness and test the *PD/PTD* theory of change with a larger diverse sample and using scalable approaches. We select a foreign low-resource country as our study site because it provides an ideal setting to test how a mental health system can be strengthened through careful consideration of strategies while simultaneously examining effectiveness outcomes of an EBI. Also, Ugandan context is similar to other underserved and under-resourced communities in the US and other LMICs. Therefore, knowledge generated from our study will be relevant globally.

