Contextual Moderators (Pre/T1 and Post PD training, and during PD implementation)	a) Outer setting: Urban/rural region (Primary moderator) b) Fidelity: 4 PD/PDT measures (F, T) c) Inner setting: School EBI climate (e.g., work environment, team work alliance, leadership) (T); d) Individual/Teacher characteristics (e.g., EBI readiness/attitude; wellness) (T) e) Intervention characteristics: Acceptability; Appropriateness (T) f) Processes: Partnership Quality (e.g., TTC and teacher/PTA partnership) (T)	b) 4 Fidelity measures  (1) Adherence (F) (deliver the core content): PD/PDT Fidelity Checklists (completed after each training day & coaching session) (2) Quality of implementation (T) (Teacher Satisfaction (T) (post PD training and T2) ( $\alpha=.72$ )  and ratings of Coaches' competence); (3) Engagement (T) Strategy Knowledge  (T) (EBI knowledge gain before-after training) (test-retest $r=.35-.43$ )  ; (4) Exposure (F): Attendance tracking  ; C) School Environment Survey  ; Organization Climate Questionnaire ( $\alpha=.65-.85$ )  d) Teacher demographic  ; PHQ-mental health  ; EBP Attitude Scale  ; e) Applied Mental Health Research Dissemination and Implementation Measurements (AMHRG)  ; f) Partnership Questionnaire 
Demo (T1)	Family/Student Demo (e.g., parenting, well-being) (P)	Family: Demo  ; Parent EBI Practices (P) ( $\alpha=.69-.80$ )  ; PHQ ( $\alpha=.90$ ) 
PD/PDT Cost	Program implementation costs;	Implementation costs: actual program costs (with & without monitoring cost) 

**Note.** For **child effectiveness outcomes**, primary data source is parent-report (P); and secondary data source is child-report/testing (C). For **teacher effectiveness outcomes**, primary data sources is classroom observation (O) & teacher report (T); and secondary data source is Parent (P) report. **CFIR contextual data** will be gathered from Training/coaching session tracking data from facilitator report (F) and teachers-report (T). **Suicidal behaviors** are NOT included because this study focuses on preventive intervention and young children (ages 4-10 years). The measures used in young children usually do not include suicidal items. However, parent, teacher, and child reported depressive symptoms will be included.

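### The Aim 2 mediation model leaves region out of the non-randomised path from teacher practice to child outcome, so a regional difference can mimic or hide mediation, to a degree that depends on how the mediator is defined

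*Combined protocol and SAP*

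**What the plan says.** The Aim 2 plan in section 9 states: "The mediation model will build on the effectiveness evaluation model (Aim 1 model". The parent model is fitted "adjusting for T1 scores and cohort". The printed Aim 2 equation is that model plus a school-level mediator M: arm (β1), time (β2), arm-by-time (β3), M (β4), cohort (β5), child T1 score (β6), and school and class random effects. Region, school size, performance, climate, leadership and the T1 value of the mediator do not appear. No covariates are named for the Sobel test or the confirmatory multilevel SEM. No assumption about mediator-outcome confounding is stated.

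The mediator is described in two ways. The narrative says the model works "by including changing scores of mediators (T2-T1) and T2 to T3 child outcome trajectory". The definition under the equation says M "is the value of the mediator at T2 and/or T3 for school".

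Elsewhere the protocol treats school context as influential. Section 1.2: "We consider geographic region (urban/ rural) as the primary moderator". Table 2 lists "Inner setting: School EBI climate (e.g., work environment, team work alliance, leadership) (T") among the contextual moderators, with measurement starting at T1. Section 4.4 has schools matched on size, location and performance. The Aim 3 plan brings moderators into the mediation model only where their interaction with intervention on a teacher outcome is significant.

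**The concern.** Randomisation protects the arm contrasts of Aim 1, where leaving out a school covariate costs only precision. It does not protect β4. Within an arm, schools differ in teacher practice for reasons nobody assigned, and anything that drives both practice and child scores enters β4 as bias. The school random intercept does not help, because the model takes it to be independent of M. Balancing region across arms does not help either, since the association at issue lies within arms.

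The protocol makes such a factor plausible: it expects region and school context to influence effectiveness. Section 14.1 also gives each region its own trainers, research assistants and classroom observers, so regional differences in rating or interviewing could reach both observed practice and parent-reported SDQ. Adjusting for the child's T1 score removes only part of a regional SDQ gap, because reliability is limited (alpha .63-.80 in Table 2).

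At stake is the Aim 2 conclusion that teacher practice, and for PDT also stress management, carries the effect on children, together with the share of the effect credited to it.

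**Working it through.** The plan gives no alpha, power or error rate for Aim 2, so there is no figure to reproduce.

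**Inputs from the protocol.** 36 schools, 12 per arm, 18 urban and 18 rural; about 15 teachers and 55 children per school; PD effect on practice d = .55-1.03 (section 1.1, Table 1); SDQ alpha .63-.80; child-effect benchmark 0.2-0.4 SD (section 9).

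**Assumptions not in the documents.** True effect of practice on children = 0; effect of arm on practice a = 0.8; SDQ reliability 0.7; true-score stability 0.8; teacher ICC 0.15; child ICC 0.03; two-sided 5%; regional gaps as stated.

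**Step 1: false indirect effect, M = T2 value.** Let the favoured region be 0.5 SD higher on practice and 0.5 SD lower on SDQ problems, with regions balanced within arm.
- T1-T2 correlation: 0.8 × 0.7 = 0.56.
- SDQ gap left after T1 adjustment (within-school slope): 0.5 × (1 - 0.56) = 0.22.
- Within-arm variance of the school-mean mediator: 0.15 + 0.85/15 + 0.5²/4 = 0.1500 + 0.0567 + 0.0625 = 0.2692.
- Covariance of mediator and adjusted outcome: -(0.5 × 0.22)/4 = -0.0275.
- False β4 = -0.0275/0.2692 = -0.102.
- False indirect effect = 0.8 × (-0.102) = -0.082 SD.

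Simulated means were 0.07-0.09 SD in size. Against the benchmark, 0.082/0.4 = 0.20 and 0.082/0.2 = 0.41. If the region with better practice has more problems, the sign flips to +0.082 and real mediation is masked. With region in both equations the covariance, and so the bias, is zero.

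For gaps of 0.3 SD (practice) and 0.2 SD (SDQ): residual SDQ gap 0.2 × 0.44 = 0.088; β4 = -(0.3 × 0.088/4)/(0.2067 + 0.0225) = -0.0066/0.2292 = -0.029; indirect effect -0.023 SD.

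**Step 2: M = T2-T1 change.** A stable practice gap is the same at both times, so it subtracts to zero and β4 is unbiased. If region shifts uptake, the gap in the change score is not zero and the bias returns.

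**Step 3: simulated false-positive rates.** School-level regression of T1-adjusted child means, true effect zero. Ranges span simulations with the same main inputs but different secondary assumptions (for example, how stable the mediator is).

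| Mediator; regional difference | β4 test, no region | Sobel, no region | With region (β4; Sobel) |
|---|---|---|---|
| T2 value; 0.5 SD on both | 28-42% | 14-28% | 5%; 3% |
| T2 value; 0.3 SD practice, 0.2 SD SDQ | 7-8% | 4-5% | not run |
| Change; stable 0.5 SD on both | 5-6% | 4% | not needed |
| Change; 0.5 SD uptake shift, 0.5 SD SDQ | 19% to about 41% | 6% to about 28% | 5%; 2-4% |

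With a 0.3 SD SDQ gap, the rates were 11-14% (β4) and 6-10% (Sobel). With no SDQ gap there was no inflation.

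**Step 4: what covariate adjustment leaves behind.** A general school factor acting after baseline, with loading 0.7 on the school component of both practice and child outcome, was simulated separately (M = T2 value, child ICC 0.08, teacher ICC 0.20, T1-T2 correlation 0.5). Sobel rejected in 44% unadjusted, 4% with the factor measured perfectly, 9% at reliability 0.7 and 16% at reliability 0.5. Region is known without error; climate and leadership are not.

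**The case against.** **Direction.** A reader might infer that any school factor raising both practice and child scores yields false support. The primary child outcomes are problem scores, so that pattern makes practice look harmful; simulated with same-sign 0.5 SD gaps, significance in the beneficial direction was 0%. The documents give no sign for a regional gap, so masking is as open as mimicry.

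**Definition.** Under the narrative's change score, the stable-region case disappears. This stands, and makes the claim conditional. But the definition under the equation permits the T2 and/or T3 value, so the exposed version is an allowed analysis.

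**Aim 3.** A reader might infer that region never reaches the mediation model. It can, through the Aim 3 step. That cover is partial: with a 0.5 SD uptake shift the interaction was significant in about 33% of simulated trials, and a stable main effect of region would not trigger it.

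**Size.** A 0.5 SD gap across 18 and 18 schools adds 0.5²/4 = 0.0625 of between-school variance, about twice the assumed ICC of 0.03. That is large, and the percentages are not forecasts for this trial.

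**Model.** The simulations use one post-baseline outcome and no time terms, whereas the plan models the T2-T3 trajectory. Figure 5 is not in the copy reviewed, so covariates drawn there cannot be excluded. Neither point changes the printed equation.

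**A nearer fault.** The plan admits mediators selectively ("Only intermediate outcomes that show significant improvement will be examined in the mediation model testing") and then says significant β1 and β3 "in the mediation model will suggest a mediation effect". Those are direct arm terms. With no confounding and no mediator effect, β1 alone was significant in 34-85% of simulated trials with a 0.3 SD direct effect. This is a separate defect, and adding region does not cure it.

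**Conclusion.** The concern holds in conditional form. As printed, the Aim 2 equation leaves the mediator-to-child path open to confounding by region, the factor the trial stratifies on and names as its primary moderator. That follows from the text and needs no assumed figure. A stable regional difference suffices if M is the T2 and/or T3 value; if M is the change score, the factor must shift uptake.

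The size does rest on assumptions: Sobel false positives of roughly 14-28% at 0.5 SD gaps with the T2 value, against about 3% with region in the model, and close to nominal at 0.2-0.3 SD.

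The documents do not show that such gaps exist, that false support is more likely than masking, or that Aim 1 is affected. Randomisation protects the Aim 1 contrasts.

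**What to change.** 1. Reconcile the two mediator definitions in the Aim 2 plan and name one as primary.
2. Add region to the mediator equation, the child-outcome equation and the multilevel SEM. If M is the T2 value, add the T1 mediator value too. The T1 school-mean EBI climate score is an optional further term; with 36 schools the list must stay short.
3. Report the adjusted indirect effect as the main Aim 2 result and the unadjusted one as a sensitivity analysis.
4. If region-by-intervention goes into the mediator equation, the indirect effect becomes region-specific; state that it is averaged equally over the two regions.
5. State that the result assumes no unmeasured mediator-outcome confounding, and give a sensitivity analysis, such as the residual correlation at which the indirect effect reaches zero.

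The cost is SAP wording and terms on variables already available at T1. The child-outcome model has about 36 - 5 = 31 school-level degrees of freedom (intercept, two arm terms, cohort, mediator), and the change uses one to three of them. Of these changes, only the region term and adjustment for a single school factor were simulated.
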